Sample Size Power Analysis: Aim 1&2, H1.1-H1.2 & H2.1 estimates of statistical power are based on Aim 1 and initially the primary outcome of pain. Whereas dyad is the unit of randomization, we assess power based on separate analyses for Veterans and partners (one approach used). There are 4 major intervals of assessment (baseline, 1, 2, and 4-months). At the beginning of this study, we estimated attrition based off of a previous MR trial that had less than 5% attrition. Based on early recruitment at the primary site, we have adjusted recruitment goals to allow for approximately 33% attrition, and uneven recruitment across the three study sites. Assuming within-subject (outcome measurement) correlation of 0.5, the proposed sample size will provide 80% power (2-sided type I error rate of 0.05) to detect a “small-to-medium” effect size of 0.38 (Cohen’s d). For analyses stratified by site (in addition to evaluation by random effect assessment), the study will provide 80% power to detect a “medium-to-large” effect size of 0.66. By way of comparison, the pilot data presented above describes large effect sizes ($d = 0.81$ for pain symptom reduction). While this effect size was based on a relatively small sample of comparable patients ($n < 15$) and within-subject assessment (paired t -test), it provides good assurance that the proposed sample size is sufficient to detect realistic, medium size effects should they exist with the MR program. For secondary outcomes, we will use a type I error rate of 0.01 for multiple comparisons. For the sample and our described assumptions, this will provide 80% power to detect a “medium” effect size of 0.45.⁵⁹

Sample Size: Qualitative- Aim 3 sample size relies on the quality and richness of information obtained.⁶⁰ Conceptual saturation is the goal of qualitative research, and depends on data to support interpretations. Saturation has been noted to occur within the first 12 interviews.^{60,61} Our team has extensive experience in evaluating electronic technologies, and have found recruiting high and low volume users provides the richest dataset. To ensure representative data, we will conduct telephone interviews with a purposive (e.g., high or low MR utilization group) sub-sample of up to 84 individuals to achieve representation at each site (approximately 28 individuals/site).

Data Collection Procedures. Data will be collected using (1) self-report surveys; and (2) telephone interviews.

(1) Self-reported Survey Data.

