Interviewers will solicit respondents' attitudes, opinions, and reports about their preferences and the pros and cons of MR and/or participating in the practice groups, including their perceptions of usefulness. We will use standard communication techniques to stimulate discussion, with prompts (e.g., "tell me more"), summarizing statements, and silence. We have used these methods in several previous studies to gather data effectively. Additionally, in an effort to understand the factors that contribute to study attrition, a maximum of ten individuals who did not complete study activities may be contacted for a brief 15-minute voluntary telephone interview. These interviews will solicit respondents' experiences with the study and any difficulties that they experienced. Only participants who were lost to follow up and who had been assigned to the treatment arm will be contacted for these attrition interviews. Participants who officially withdrew from the study will be excluded from the pool of prospective interviews.

A total of 84 interviews (n=84 individuals), including participants lost to follow up and participants who have successfully completed the study, will be performed. We will attempt to interview both members of dyads to obtain conceptual saturation.

Data Analysis: The *intention to treat* principle will be used for all analyses irrespective of the extent of protocol compliance or dropout.⁹⁰ Whereas randomization is anticipated to balance both study arms on presenting demographic and clinical characteristics, including

within sites and by concomitant receipt of first line pain and/or PTSD treatment, continuous variables will be compared by student t-tests or Wilcoxon tests (depending on distributional properties); categorical variables will be compared by chi-square analyses.

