Hypotheses Aims 1 & 2. All outcome measures (*primary and secondary*) under Aim 1 will be collected at baseline, 1, 2, and 4 months and are continuous variables. Therefore, general linear mixed models will be used with main effects terms for GROUP (MR vs. waitlist) and TIME (4-time points) and a GROUP x TIME interaction term (for rate of change). The models will also include site as a random effect. To assess whether the rate of change is curvilinear (i.e., the rate of change differs between time points), a quadratic parameter will be tested. Different correlation structures and functional forms of the effects of the MR program will be assessed using the information criteria and a final parsimonious model will be determined for final statistical inference. Initial effects of the MR program (baseline to 1-month) will be evaluated by analysis of covariance (ANCOVA). For H1.1, the primary outcome measure for pain will be total score on the 19-item POQ. For H1.2., the primary outcome measure for PTSD will be total score on the 20-item PCL-5. Subgroup analyses will be explored using similar methods and examination of severity of baseline pain and PTSD scores. These analyses will provide insight into subgroups in whom the MR program may be particularly beneficial. In a similar realm, analyses will be stratified by baseline median level of relationship satisfaction, as derived from total score on the 14-item RDAS. This will permit assessment of the effect of the MR intervention on potential improvement in relationship satisfaction among a cohort of dyads with presumably troubled relationships at entry. Moreover, using the weekly reports (8 weeks) of MR use and satisfaction with the MR program, the MR sample will be split above versus below the median for these two measures, and compared separately against the waitlist control condition at 2-months. This approach approximates a “per protocol” analysis in terms of recommended use of the MR program. In addition, especially for Aim 2 outcomes, we seek to examine whether dyads appear to show mutual benefits from the MR program. Therefore, multilevel models will be fit using an over-time dyadic model⁷⁸ in which individuals are nested within dyads and time is crossed with dyads (i.e., both Veteran and partner are assessed at the 4 time points). This analysis accounts for the non-independence due to the correlation between dyad members’ general levels on outcomes averaged over time, as well as the time-specific correlation between their outcomes (e.g., similarity caused by time-specific events).

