Missing data. Missing data will be tabulated by treatment arms and by assessment waves; comparison tests between arms will be conducted to assess potential attrition bias and to examine the missing data mechanism (e.g. missing at random). If missing rate is less than 10%, analyses with list wise deletion (missing values dropped from the analysis) will be performed (due to minimal concern over bias). Participants who are lost to follow-up and missing on post randomization outcome assessments will be included in additional comparison analyses that utilize multiple imputations of missing data to minimize bias due to differences between those with complete and incomplete data.

Dissemination Plan. Dissemination efforts will be led by the PI along with the VA operational (e.g. OPCCCT and CCO), clinical stakeholders (e.g. mental health and pain clinicians), and the Tampa R&DS VEC. We will publish findings in peer-reviewed journals and present findings at national and international meetings including Medicine 2.0, the international conference for internet-based health research ([name]) and Association of Military Surgeons of the United States (AMSUS) Annual Continuing Education Meeting. Dissemination activities will inform VHA operational initiatives and clinical practice (Table 2). The deployment of Whole Health models of care nationally will provide a natural setting for dissemination. The Tampa VEC will support dissemination efforts to Veterans, their families, and to Veteran Service Organizations.

Table 2. Dissemination Plan

Format	Target Audience	Potential Use or Outcomes
1. Mission Reconnect for Veterans and their partners		
Briefing	Clinicians in Mental Health and Pain Clinics, VEC	
 • MR as an option for non-pharmacological self-care management for chronic pain
2. Linking study findings to operational and clinical initiatives		
Reports/Oral Presentation	Office of Mental Health	
 • Guidelines for using MR to support clinical care
	Connected Care Office	
 • Support operational mission and provide insight on usability and application of MR
	Office of Patient Centered Care & Cultural Transformation &	
 • Support operational mission and provide insight on usability and application of MR

Flagships		• Lessons learned and MR use strategies
3. Mission Reconnect in the VA for self-care management		

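### The missing-data rule conflicts with intention to treat: listwise deletion applies when an undefined missing rate is below 10%, and no primary method is stated at the roughly 33% attrition now planned for

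*Combined protocol and SAP*

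**What the plan says.** The Data Analysis section of the protocol states that the intention-to-treat "principle will be used for all analyses irrespective of the extent of protocol compliance or dropout". For the outcomes it then specifies that "general linear mixed models will be used with main effects terms for GROUP (MR vs. waitlist) and TIME (4-time points" together with their interaction. It does not say how a participant with missing visits enters that model.

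The Missing data paragraph, under Data Management and Quality, has missingness tabulated by arm and by wave and then gives the operative rule: "If missing rate is less than 10%, analyses with list wise deletion (missing values dropped from the analysis) will be performed", the reason being "due to minimal concern over bias". Its last sentence says that participants lost to follow-up and lacking outcomes "will be included in additional comparison analyses that utilize multiple imputations of missing data".

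The Sample Size Power Analysis paragraph records that the starting expectation was attrition below 5%, and that "we have adjusted recruitment goals to allow for approximately 33% attrition".

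The Updated Statistical Analysis Plan keeps the mixed model, now with continuous time. It contains no analysis set and no missing-data rule, so the protocol paragraph still stands.

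**The concern.** Two analysts could follow this plan faithfully and analyse different people. One would fit the mixed model to every randomised participant's observed visits, citing intention to treat. The other would remove every participant with a missing visit, citing the Missing data paragraph. The documents do not say which analysis is primary, or which missing rate decides the matter.

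Whole-case deletion turns H1.1 into a comparison among completers, which randomisation does not protect. Dropout that differs by arm is plausible: one arm is asked to practise a programme, while the other gets access to it after completing data collection. The attrition level now allowed for is the one for which no primary handling is written, so the method could end up being chosen after the data are seen.

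**Working it through.** **1. The rules side by side.**

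| Missing rate | Intention-to-treat sentence | Missing data paragraph | Updated SAP |
|---|---|---|---|
| Below 10% | all participants, whatever the dropout | listwise deletion | silent |
| 10% or more | all participants, whatever the dropout | no primary method; imputation is additional | silent |

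**2. Which rate triggers the switch.** Suppose 0%, 2%, 4% and 33% are missing at baseline and months 1, 2 and 4 (assumed).
- Pooled over four visits: (0 + 2 + 4 + 33)/4 = 9.75%, so listwise deletion applies.
- Pooled over follow-up visits: (2 + 4 + 33)/3 = 13%, so it does not.
- At month 4 alone: 33%, so it does not.

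Likewise, 19.8% missing in one of two equal arms and none in the other pools to 9.9%. The unstated definition decides the branch.

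**3. Bias of a completer comparison.** In one arm, let m be the share missing and D the mean of dropouts minus the mean of completers, in SD. The completer mean equals the full mean minus m·D, so the bias in MR minus waitlist is −(m_MR·D_MR − m_W·D_W). It is zero if D is zero, or if m and D are the same in both arms. With a common D between 0.25 and 1.0 (assumed), an unadjusted difference in means is biased by:
- 9.9% overall, split 2:1 (13.2% and 6.6%): 0.066 × D = 0.02 to 0.07 SD
- 9.9% overall, all in one arm: 0.198 × D = 0.05 to 0.20 SD
- 33% overall, split 2:1 (44% and 22%): 0.22 × D = 0.06 to 0.22 SD

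**4. Simulation.** From the plan: 300 per arm (600 dyads, 1:1), within-subject correlation 0.5, visits at baseline and months 1, 2 and 4. Assumed: SD 1, and monotone dropout depending on the last observed score with log-odds slope 0.7 per SD. Complete-case ANCOVA of month 4 on baseline is compared with maximum likelihood on all observed visits. Negative values favour MR.

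| Dropout pattern | True effect | Complete case | False positives | Likelihood |
|---|---|---|---|---|
| Opposite slopes, about 37% lost steadily | 0 | −0.096 | 17% | 0.002 (5%) |
| Opposite slopes, loss mostly at month 4 (33%) | 0 | −0.105 | 22% | 0.000 |
| Same late-loss pattern | −0.38 | −0.483 | not applicable | −0.378 |
| Late loss, slope in MR only | 0 | −0.050 | 9% | not run |
| Late loss, same slope in both arms | 0 | −0.001 | 4.8% | not run |
| Opposite slopes, about 10.5% lost in total | 0 | −0.026 | about 6% | not run |

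Independent reruns of the two opposite-slope, heavy-loss patterns gave 0.087 to 0.109 SD and 17% to 25% false positives. With 109 per arm the late-loss figure falls to 12%. Steeper opposite slopes (1.0 per SD, about 32% lost) turned a true −0.38 into about −0.52, a bias of 0.14, so 0.1 is not a ceiling.

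**5. The planned slope behaves differently.** The times 0, 1, 2 and 4 have mean 1.75, deviations −1.75, −0.75, 0.25 and 2.25, and sum of squares 8.75. Suppose selection on one visit shifts completers by s there and, with correlation 0.5, by 0.5s at the other visits.
- Selection on month 2 (late loss): (−0.875 − 0.375 + 0.25 + 1.125)s/8.75 = 0.014s per month, close to zero.
- Equal selection on baseline, month 1 and month 2 (steady loss): (−0.875 − 0.375 + 0.125)s/8.75 = −0.129s per month. With s negative in MR and positive in waitlist, this runs against MR.

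Simulation of the linear group-by-time slope gave the same pattern.

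The plan gives no bias figure to reproduce. Its detectable effect of 0.38 serves here only as a yardstick.

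**The case against.** The strongest reply is that the text can be read benignly. The paragraph glosses its own term as dropping missing values. In a long-format mixed model this removes unobserved visits and keeps the participant, which is close to what is recommended below. It also never says that those lost to follow-up leave the main model; "Participants who are lost to follow-up and missing on post randomization outcome assessments will be included in additional comparison analyses that utilize multiple imputations" adds an analysis without forbidding another. Both points stand. Listwise deletion ordinarily means whole cases, however, so the text is at best ambiguous.

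The second reply concerns size. The simulated estimator is not the planned one: the protocol uses ANCOVA only for baseline to month 1, and no section names month 4 as the primary time point. At about 33% loss, the 10% branch applies only if the rate is pooled over waves including baseline, and the sentence before the rule has missingness tabulated by wave. Within the branch's natural range the bias is about 0.03 SD under the simulated dropout model, which broadly supports the protocol's view that bias is a minor concern there. These points stand too. They limit the bias claim but do not remove the conflict or supply the missing rule at 10% or more.

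A reader might also infer that withdrawn participants belong to no analysis set, because "Participants who officially withdrew from the study will be excluded from the pool of prospective interviews". The documents do not support this. That sentence decides whom to call for attrition interviews. The statements on formal exclusion, in the PTSD training and adverse event sections, concern further participation, and the intention-to-treat sentence still covers everyone. A link between the 10% threshold and the earlier attrition estimate below 5% would likewise be conjecture.

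**Conclusion.** The concern holds as a conflict and a gap in the plan. Intention to treat whatever the dropout and listwise deletion below 10% cannot both govern if deletion is of whole cases. The rate is undefined, the updated SAP does not settle the matter, and no primary method exists for the attrition now allowed for.

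The consequence is conditional. Bias is near zero if dropout is unrelated to outcome, or has the same rate and dependence in both arms. It is about 0.03 SD at roughly 10% total loss (0.03/0.38 = 8% of the detectable effect). It is about 0.1 SD (0.1/0.38 = 26%) for a month-4 complete-case contrast with about a third lost and opposite slopes of 0.7 by arm. Wider assumptions give wider values, as shown. For the planned slope the bias may be nil or run against MR.

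The 17% to 22% false-positive rates belong to an assumed worst case for a month-4 complete-case ANCOVA. A reader might take them as the trial's expected error rate, or conclude that the plan favours MR; the documents support neither. The likelihood results assume that missingness depends only on observed data.

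**What to change.** In the Missing data paragraph and in the updated SAP, delete the 10% switch and listwise deletion, and state:

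*The primary analysis of H1.1, H1.2 and H2.1 is the likelihood-based mixed model fitted to all observed visits of every randomised participant, by assigned arm, using data up to any loss to follow-up, withdrawal or exclusion, whatever the missing rate. Multiple imputation is a sensitivity analysis covering all participants with missing outcomes.*

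Missingness should still be reported by arm and wave, but should no longer select the method. Both methods assume missingness at random, so a prespecified sensitivity analysis for departures from it would be a sensible addition, as would a line on how the month-1 ANCOVA treats missing scores.

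The cost is wording: the model is already planned, and no new data or participants are needed. The updated SAP reports the qualitative coding in the past tense, so the amendment should be dated and should say whether outcomes by arm had been examined.
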